## 5.5 Subject Withdrawal

### 5.5.1 Reasons for Withdrawal

Subjects are free to withdraw from participation in the study at any time upon request, as outlined in the consent form documents.

Participants who drop out (or withdraw) from the study by their own choice will be considered dropouts/withdrawals. Participants who are discontinued from the study by one of the study personnel will be also be considered a dropout/withdrawal.

An investigator may terminate a study subject's participation in the study if:

- Any clinical adverse event (AE), laboratory abnormality, or other medical condition or situation occurs such that continued participation in the study would not be in the best interest of the subject.
- The subject meets an exclusion criterion (either newly developed or not previously recognized) that precludes further study participation.

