## 2.3 Potential Risks and Benefits

### 2.3.1 *Potential Risks*

Study Interventions: SDF was introduced in the US in 2015 and approved by the FDA as a medical device; the high viscosity glass ionomer cements (GIC) used in ART were introduced in the 1970s. All of the interventions are in current clinical use for package inserts for SDF, ART with GIC, FV). The study interventions are non-invasive and does not require the use of conventional drilling procedures. There is risk of hypersensitivity to silver or fluoride from the 38% SDF. SDF can stain the gums or oral mucosa or tooth colored fillings. There is minimal risk with the ART and FV applications (**RQ-5**).

Dental exams: The project will involve clinical dental exams for the participants. The dental exams do not pose any additional risks to participants beyond those encountered in daily living. Dental examinations will be visual/tactile using a probe and non-invasive. No x-rays will be taken.

Interviews: Some people are uncomfortable answering questions about themselves for research. We will try to make participants feel as comfortable as possible. There is also a chance that confidential information can be lost but we will use every precaution to protect the information. To protect the privacy of participants, a unique ID number will be used. The connection between this code number and participant’s identity will be confidential and will be required to link the contact form, questionnaires and dental data. Only project staff members will have access to these codes and identifying information. Once the study data collection is completed, the link between the individual and their data will be destroyed.

Focus groups: There is little risk to participants during the focus group discussions. While it is unlikely, some participants may feel shy or embarrassed by some of the questions asked during the meetings or interviews. The facilitator and moderator will make every effort to put participants at ease and to communicate to them that any information shared during the discussions and interviews would not be relayed to others. Further, any names or other identifying information will be removed during the transcription process and will not appear in the final transcripts of the discussion groups. All audio files will be deleted after they are transcribed.

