### 5.2 Subject Exclusion Criteria

Following the dental screening, further exclusion criteria for non-eligibility to participate in the RCT include:

- Sensitivity to silver or other heavy-metal ions
- Those with ulcerative gingivitis or stomatitis which prevents them from receiving study treatment
- Serious life-threatening medical disease

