### **5.5.2 *Handling of Subject Withdrawals or Subject Discontinuation of Study Intervention***

All reasons for dropout/withdrawal or discontinuation of the study intervention will be documented in the tracking database and reviewed by the study team and reported to the DSMB. For gathering information on discontinuation, study staff will be contacting participants at several time points. Study staff will contact participants by phone 2-3 days before all exam and treatment visits to remind participants of the appointment, 2-3 days before all one-on-one interview appointments for survey completion, and 24 hours after all dental exam and treatment visits to complete the safety questionnaire. Participants will also be seen in person for all exam and treatment appointments and one-on-one interview appointments for survey completion.

In the event of a subject telling study staff that he/she is dropping out of the study, the study staff should gather the following information as much as the participant allows.

- Record the reason for dropping out of the study.
- Record any adverse event reported by the subject.
- Complete the appropriate questionnaire nearest the drop out time point.

If it is determined by study staff that a participant should be discontinued from the study, the decision to withdraw a participant must be discussed and confirmed by the PI.

Participants that withdraw during the baseline data collection window will be replaced by recruitment of additional participant to reach enrollment goals. Participants that withdraw or that are lost to follow-up any time after the baseline data collection window will not be replaced, but data collected up to the point of withdrawal will be used for analysis.

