Secondarily, we will extend the above GEE approach to analyze the repeated (baseline, 26 and 52-week) measures for each outcome. The models for each outcome will include the same prognostic variables as before, as well as time and a time by treatment interaction. We will allow for correlations among the repeated measures, e.g., using a first-order autocorrelation structure. If a substantial within-facility correlation is found we may need to incorporate facility as a second cluster levels (within which person – the first cluster level – is nested). We will estimate and test (via a robust t-test) the interaction term to compare trends over time for the two interventions. If the use of two cluster levels is not found to be feasible in the GEE approach, we will consider a generalized mixed effects model approach.

**Causal Inference standards (CI-1, CI-2, CI-3, CI-4):** Our use of randomization and adjustment in regression models should be sufficient to provide causally interpretable intervention effect estimates; special causal inference techniques such as propensity score or instrumental variable methods often indicated for observational studies, will therefore not be necessary for our data analysis. We will avoid biases in causal inferences about the intended interventions by using an intent-to-treat approach, in which individuals are analyzed according to randomized groups without regard to (extent of) treatment actually received.

**Sensitivity Analyses IR-5:** We will check sensitivity of conclusions to model assumptions as well as methodological decisions such as outcome definition. In particular, for the arrest outcome, our primary analysis is based on a binary indicator of 'complete' arrest of all lesions for an individual. We will seek to corroborate results from this approach with an alternative approach analyzing

number of lesions arrested. For the GEE analyses, planned for all outcomes, sensitivity will be assessed in part by using alternative working covariance structures and alternative sets of predictors. For some outcomes, alternative distributions will be considered; for example, for number of arrested lesions, possible distributions include Poisson, negative binomial, zero-inflated Poisson (ZIP), and zero-inflated negative binomial (ZINB). Sensitivity to assumptions regarding missing data will also be investigated as described further below.

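### Sections 5.5.1, 5.5.2 and 7.4 end outcome follow-up whenever study staff end participation, and silver sensitivity can make that loss differ by arm

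*Combined protocol and SAP*

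**What the plan says.** Section 5.5.1 gives two grounds on which an investigator may terminate a subject's participation in the study. The first is an adverse event, laboratory abnormality or other medical condition that makes continuing not in the subject's interest. The second is: "The subject meets an exclusion criterion (either newly developed or not previously recognized) that precludes further study participation". The same section adds: "Participants who are discontinued from the study by one of the study personnel will be also be considered a dropout/withdrawal".

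For withdrawals after the baseline window, section 5.5.2 says that "data collected up to the point of withdrawal will be used for analysis". Section 7.4 covers those whose participation the principal investigator terminates as well as those who choose to leave. It closes visits and data collection on withdrawal and treats the person as lost to follow-up, with questionnaires at withdrawal where applicable.

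The exclusions in section 5.2 include "Sensitivity to silver or other heavy-metal ions" and "Those with ulcerative gingivitis or stomatitis which prevents them from receiving study treatment". Section 2.3.1 states: "There is risk of hypersensitivity to silver or fluoride from the 38% SDF". It describes the risk of ART and FV as minimal.

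Section 11.4 adopts intent-to-treat, under which "individuals are analyzed according to randomized groups without regard to (extent of) treatment actually received". It also says that the primary analyses assume outcomes missing completely at random, with multiple imputation as the support when they are not.

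**The concern.** Both grounds in section 5.5.1 end study participation, so a decision about treatment also ends measurement of the outcome. The heading of section 5.5.2 mentions discontinuation of the study intervention, but no section provides 26- or 52-week assessments for someone who stops treatment and stays in the trial.

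The trigger can be linked to arm. The treatment steps apply silver only in Arm 1, so a sensitivity brought on or revealed by study treatment can arise only there. (The Arm 2 heading in section 6.2 names the SDF product, but none of the steps under it apply it.) A reaction to SDF could fall under either ground.

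At stake are the 52-week arrest and pain comparisons. An intent-to-treat comparison needs outcomes from people who stopped treatment, and this rule stops their collection. Loss caused by a reaction to the assigned treatment is not missing completely at random. In a non-inferiority trial, selective loss of poor SDF outcomes would move the estimate toward the claim.

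**Working it through.** **The rule, followed through.** Suppose a silver sensitivity comes to light after the baseline SDF application. Section 5.5.1 permits termination and classes the person as a dropout/withdrawal. Section 5.5.2 limits the analysis to data already collected, and section 7.4 ends visits. The 52-week arrest exam is not done. Pain may be asked once at withdrawal, but not at 52 weeks.

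**The plan's power figures (section 11.2).** Inputs: 275 per arm in 11 sites, 15% dropout, ICC 0.01 or 0.02, one-sided alpha 0.025; pain margin 8 and SD 25; arrest 90% in both arms with margin 0.09.

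- Evaluable per arm: 275 × 0.85 = 233.75, or 233.75 / 11 = 21.25 per site.
- Design effect at ICC 0.01: 1 + (21.25 − 1) × 0.01 = 1.2025. Effective n = 233.75 / 1.2025 = 194.4.
- At ICC 0.02 the design effect is 1.405 and effective n is 166.4.
- Pain power: Φ(8 / [25√(2/194.4)] − 1.96) = 88.4% (plan 89%). At ICC 0.02 it is 83.1% (plan 83%).
- Arrest power: Φ(0.09 / √(2 × 0.9 × 0.1 / 194.4) − 1.96) = 84.1% (plan 85%). At ICC 0.02 it is 78.1% (plan about 80%).

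All four agree within 2 points. The sample-size figures stand, and this point does not touch them.

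**Illustration for arrest.** Assumptions: true arrest is 0.81 for SDF and 0.90 for ART+FV, exactly at the margin; ICC is 0.01; a fraction q of Arm 1 is removed and nobody from Arm 2; those removed have arrest proportion r. The documents give neither q nor r.

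- Observed SDF rate: p = (0.81 − q·r) / (1 − q). Bias = p − 0.81.
- SE = √(0.90 × 0.10 / 194.4 + p(1 − p) / [194.4(1 − q)]).
- False non-inferiority rate = Φ(bias / SE − 1.96). At q = 0 it is 2.5%.

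Worked case, q = 1% and r = 0: p = 0.81 / 0.99 = 0.8182, bias = 0.0082, SE = 0.0352, and Φ(0.233 − 1.96) = 4.2%.

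| Arm 1 removed | People | None arrested (r = 0): difference, error | Half arrested (r = 0.5): difference, error | Like their arm (r = 0.81): error | All arrested (r = 1): error |
|---|---|---|---|---|---|
| 1% | about 2 | −0.082, 4.2% | −0.087, 3.1% | 2.5% | 2.2% |
| 2% | about 5 | −0.073, 6.9% | −0.084, about 3.7% | 2.5% | 1.9% |
| 3% | about 7 | −0.065, 10.8% | −0.080, 4.6% | 2.5% | 1.7% |

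**Illustration for pain.** Let the true difference be 8 and let those removed have a mean change D mm worse than their arm. The estimate shifts by about q × D in favour of SDF. With D = 25, removing 1% or 2% shifts it by 0.25 or 0.5 mm and gives an error of 3.1% or 3.9%. With D = 10 the errors are 2.7% and 3.0%.

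**The case against.** The rule is permissive, and its second ground applies only where the criterion precludes further participation. Section 5.5.2 requires the principal investigator to confirm staff-initiated withdrawals, records the reasons and reports them to the DSMB. Section 11.4 plans to compare missing-outcome rates between arms, to test missingness against early outcomes, and to use multiple imputation with alternative models. Any 26-week data remain usable in the repeated-measures model.

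This stands as mitigation, but none of it recovers a 52-week outcome. Imputation would have no outcomes from people taken off treatment by this route. The roughly 40 who missed the second dose through COVID-19 restrictions missed it for another reason.

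Three stronger readings are tempting, and the objection to each succeeds.

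- A reader might infer that SDF also brings on stomatitis, making two exclusions arm-linked. On soft tissue, section 2.3.1 says only that "SDF can stain the gums or oral mucosa or tooth colored fillings", which is not stomatitis. The section 5.2 criterion applies only when the condition prevents treatment, and Appendix A schedules the soft-tissue check without distinction by arm. Only the silver criterion is supported.
- A reader might infer that the loss favours SDF. Nothing in the documents links silver hypersensitivity to unarrested lesions or worse pain, and these participants would have had their eligible lesions treated at baseline. Missing the 26-week application makes that direction plausible, but does not establish it.
- A reader might infer that the plan flatly contradicts intent-to-treat. Withdrawn people stay in their randomized group with the data they have. The defect is that their later outcomes are not collected.

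**Conclusion.** The point holds as a gap in outcome collection. Sections 5.5.1, 5.5.2 and 7.4 tie the end of treatment to the end of follow-up, and a documented SDF risk can make the resulting loss differ by arm. That undercuts the intent-to-treat aim and the missing-data assumption in section 11.4.

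Direction and size are unknown. The 4.2%, 6.9% and 10.8% error rates are an unfavourable bound: they need every removed participant to be non-arrested, every removal to be in Arm 1, and the truth to lie on the margin. If half had arrest, the rates are about 3.1%, 3.7% and 4.6%. If those removed resemble their arm there is no bias, and if they do better the bias runs against SDF. The numbers may well be small. The case for acting is that the remedy is cheap and the lost outcomes cannot be rebuilt later.

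**What to change.** In section 5.5.1 (both grounds), section 5.5.2 and section 7.4, word the stopping of study treatment separately from the ending of outcome collection. State that a participant treated at baseline whose study treatment is stopped by study personnel keeps the 26- and 52-week exams and questionnaires and stays in the intent-to-treat analysis, unless that person withdraws consent or cannot be examined.

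In section 11.4, commit to reporting investigator terminations by arm and reason, and add a sensitivity analysis that counts terminated SDF participants as non-arrested. Both also serve for anyone whose follow-up has already ended under the present wording.

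The change concerns outcome collection only. When treatment should stop remains a clinical decision for the protocol. The cost is amendment wording, a few extra exams and surveys at site visits already scheduled, and one further analysis.

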### **5.5.2 *Handling of Subject Withdrawals or Subject Discontinuation of Study Intervention***

All reasons for dropout/withdrawal or discontinuation of the study intervention will be documented in the tracking database and reviewed by the study team and reported to the DSMB. For gathering information on discontinuation, study staff will be contacting participants at several time points. Study staff will contact participants by phone 2-3 days before all exam and treatment visits to remind participants of the appointment, 2-3 days before all one-on-one interview appointments for survey completion, and 24 hours after all dental exam and treatment visits to complete the safety questionnaire. Participants will also be seen in person for all exam and treatment appointments and one-on-one interview appointments for survey completion.

In the event of a subject telling study staff that he/she is dropping out of the study, the study staff should gather the following information as much as the participant allows.

- Record the reason for dropping out of the study.
- Record any adverse event reported by the subject.
- Complete the appropriate questionnaire nearest the drop out time point.

If it is determined by study staff that a participant should be discontinued from the study, the decision to withdraw a participant must be discussed and confirmed by the PI.

Participants that withdraw during the baseline data collection window will be replaced by recruitment of additional participant to reach enrollment goals. Participants that withdraw or that are lost to follow-up any time after the baseline data collection window will not be replaced, but data collected up to the point of withdrawal will be used for analysis.

### **5.6 Premature Termination or Suspension of Study**

This study may be suspended or prematurely terminated if there is sufficient reasonable cause. Written notification, documenting the reason for study suspension or termination, will be provided by the suspending or terminating party to investigator, funding agency, the Investigational New Drug (IND) /Investigational Device Exemption (IDE) sponsor and regulatory authorities>. If the study is prematurely terminated or suspended, the principal investigator will promptly inform the IRB and will provide the reason(s) for the termination or suspension.

Circumstances that may warrant termination include, but are not limited to:

- Determination of unexpected, significant, or unacceptable risk to subjects.

---

- Insufficient adherence to protocol requirements.
- Data that are not sufficiently complete and/or evaluable.
- Determination of futility.

## 6 STUDY INTERVENTION

### 6.1 Study Product Description

None of the materials used in this study are experimental. All materials are cleared by the FDA as Class II medical devices. All of the study materials will be donated by the manufacturers.

Study Arm 1:

- Advantage Arrest. This is an aqueous solution of 38% silver diamine fluoride, tinted blue.

Study Arm 2:

- GC Fuji Automix LC. This is a radiopaque light cured resin reinforced glass ionomer restorative.
- Cavity Conditioner. Mild aqueous polyacrylic acid solution
- GC Fuji COAT LC. This is a light cured protective coating.
- FluoriMax Varnish. This is sodium fluoride in an alcohol solution of natural resins.

#### 6.1.1 *Formulation, Packaging, and Labeling*

Study Arm 1:

- Advantage Arrest. This is an aqueous solution of 38% silver diamine fluoride, tinted blue. Packaging and labeling are not modified from the commercial product. This product is packaged in individual dosettes, with one dosette used per patient.

Study Arm 2:

- GC Fuji Automix LC. This is a paste/paste formulation that is packaged in the original automix syringe. Packaging and labeling are not modified from the commercial product. Each syringe is expected to provide about 10 restorations.
- Cavity Conditioner. Dispensed in a 5.7 ml multi-use vial. Packaging and labeling are not modified from the commercial product.
- GC Fuji COAT LC. This is a light cured protective coating. Packaging and labeling are not modified from the commercial product. Each bottle holds 5.2 ml of product.
- FluoriMax Varnish. This is sodium fluoride in an alcohol solution of natural resins. Packaging and labeling are not modified from the commercial product. This varnish is packaged in individual dosettes, with one dosette used per patient.

#### 6.1.2 *Product Storage and Stability*

Study Arm 1:

- Advantage Arrest. Product is to be stored in a cool, dark place (4-25 C). It has a shelf life of 3 years from the date of manufacture. Individual dosettes should be discarded after use.

Study Arm 2:

- GC Fuji Automix LC. Product is to be stored in a cool, dark place (4-25 C). It has a shelf life of 2 years from the date of manufacture.
- GC Fuji COAT LC. Product is to be stored in a cool, dark place (4-25 C). It has a shelf life of 2 years from the date of manufacture.
- Cavity Conditioner (GC). Product is to be stored in a cool, dark place (4-25 C). It has a shelf life of 3 years from the date of manufacture.
- FluoriMax Varnish. Product is to be stored in a cool, dark place (4-25 C). It has a shelf life of 3 years from the date of manufacture. Individual dosettes should be discarded after use.

## 6.2 Dosage, Preparation and Administration of Study Product

### Study Arm 1:

Advantage Arrest. The application procedure is below:

1. The cavity will be cleaned with a dry manual tooth brush to remove debris.
2. The area will be isolated with cotton rolls. If the lesion is at the gumline, the gingiva will be coated with a thin layer of petroleum jelly per manufacturer's instructions.
3. The single use SDF vial (Advantage Arrest, Elevate Oral Care) will be opened and the manufacturer's supplied brush will be dipped into the reservoir. The SDF will be applied with the brush until the lesion is coated fully.
4. Allow to air dry. The patient can resume normal activity with no restriction.

### Study Arm 2:

GC Fuji and Advantage Arrest. The application procedure is below:

1. The cavity will be isolated and dried
2. Any debris and soft, demineralized tooth structure from cavitated lesions will be removed with spoon excavators as necessary and protecting the pulp. No local anesthesia will be used.
3. The cavity will be cleaned next with a *manual* brush and pumice or a toothbrush or cotton roll.
4. Application of polyacrylic acid conditioner to the cavity and rinsing (Cavity Conditioner (GC)).
5. The area will be moisture controlled before placement of resin reinforced glass ionomer restoration (GC Fuji Automix LC) with an applicator gun. Next the finger will be used to compress the material into the cavity.
6. After the GIC material is placed, GC Fuji COAT LC will be used.
7. The occlusion will be checked and cleared using articulating paper.
8. The GIC application will be light cured.

More details about the step by step procedure is given in Section 6.10.

### **6.3 Modification of Study Product Administration for a Subject**

The study products' administration are not being modified.

### **6.4 Accountability Procedures for the Study Product**

The study products will be stored in a locked storage area. The principal investigator (or her delegate) will maintain an inventory system to account for study products. The products will be distributed before each clinic session and unused product will be maintained in the field units. The materials will only be used by licensed personnel.

